3.4. Stratification, Randomization, and Blinding/Masking

Randomization will be stratified by groups of study sites to ensure treatment balance based on variation in standard of care, and by baseline use of corticosteroids for treatment of COVID-19. Block randomization with random block size will be used. The randomization schedule will be generated by the un-blinded study statistician. The participants and study staff will be blinded to the treatment.

3.4.1. Procedure for Unblinding/Unmasking

Unblinding must be approved by the study Vanderbilt Corordinating Center (VCC) Medical Monitor (MM) and the DAIT/NIAID Medical Officer unless an immediate life-threatening condition has developed and the VCC MM is not accessible, in which case the treating physician is authorized to unblind the treatment for an individual participant. The site investigator should send a blinded email to the protocol chair(s), the VCC study team, VCC Medical Monitor and DAIT/NIAID Medical Officer of the unblinding event within 24 hours. The emergency unblinding will also be reported to the Data and Safety Monitoring Board (DSMB).

A full account of the event will be recorded in the EDC either in AE Form or PD Form, whichever is applicable including the date and time of the unblinding, the reason for the decision to unblind, and the name of the individual who made the decision and the names of the VCC MM and others who were notified. The reasons for unblinding of a participant's treatment will be included in the final study report.

Unblinding the study due to an approved interim analysis, final analysis, or study termination will require written approval from DAIT/NIAID.

4. Selection of Participants

4.1. Rationale for Study Population

The goal of the study is to determine whether treatment with IC14 reduces the time to resolution of COVID-19 respiratory illness. The study population will consist of participants who are hospitalized with proven COVID-19 illness, defined by a positive RT-PCR test for SARS-CoV-2 virus, respiratory symptoms compatible with COVID-19 illness, hypoxemia and one or more pulmonary infiltrates, but who are not yet requiring monitoring or support in an intensive care unit.

4.2. Inclusion Criteria

Patients may be included in the study only if they meet **all** the following criteria:

1. Patient or a responsible family member or legal representative must be able to understand and give written informed consent.
2. Age greater than or equal to 18 years
3. Presence of SARS-CoV-2 infection documented by positive RT-PCR testing or history of positive RT-PCR test for SARS-CoV-2 within 7 days of screening
4. Radiologic findings compatible with diagnosis of SARS-CoV-2 pulmonary infection with no alternative explanation for the radiologic findings
5. Hypoxemia as defined by any of the following:
 - a. $\text{SpO}_2 \leq 94\%$ on room air, or
 - b. Requirement for $\geq 2\text{L}/\text{m}$ O_2 per standard nasal cannula to maintain $\text{SpO}_2 > 94\%$, but not requiring high-flow nasal cannula (defined as $\geq 30\text{ L}/\text{m}$)
6. Women of childbearing potential must have a negative pregnancy test and be willing to use birth control for the duration of the study.

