3.2. Secondary Endpoints

3.2.1. Secondary efficacy endpoints:

1. Days-alive-and-free of any episodes of acute respiratory failure through Day-28 defined by need for the following oxygen delivery resources:
 - a. High-flow nasal cannula (flow rates \geq 30L/min with $\text{FiO}_2 \geq 0.4$)
 - b. Noninvasive positive-pressure ventilation through nasal or face mask, or nasal plugs
 - c. Endotracheal intubation and mechanical ventilation
 - d. Extracorporeal membrane oxygenation
2. Mean change in the ordinal scale from baseline to Days 14 and 28.
3. Ordinal scale value on Day 14.
4. All-cause mortality through Days 28 and 60.
5. Proportion of participants alive-and-free of any episode of acute respiratory failure through Day 28.
6. Days-alive-and-free of invasive mechanical ventilation through Day 28.
7. Proportion of participants alive-and-free of invasive mechanical ventilation through Day 28.
8. Proportion of participants alive and discharged from the hospital through Day 28.
9. Proportion of participants who begin corticosteroid therapy for worsening COVID-19 illness after randomization.

3.2.2. Secondary safety endpoints:

1. Safety of IC14 as measured by change from baseline in liver (alanine transaminase, aspartate transaminase, total bilirubin), renal (creatinine), hematological (hemoglobin, white blood cell count with differential), and coagulation function (platelets, prothrombin time) through Day 28.
2. Cumulative incidence of Grade 3 and 4 clinical and/or laboratory adverse events through Day 28.
3. Cumulative incidence of serious adverse events through Day 60.

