4.3. Exclusion Criteria

An individual fulfilling **any** of the following criteria is to be excluded from enrollment in the study:

1. Receiving non-invasive positive-pressure ventilation through nasal mask, face mask, or nasal plugs
2. Receiving invasive mechanical ventilation
3. Patient, surrogate, or physician not committed to full support (exception: a participant will not be excluded if he/she would receive all supportive care other than attempts at resuscitation from cardiac arrest)
4. Anticipated survival < 48 hours

5. Underlying malignancy, or other condition, with estimated life expectancy of less than two months
6. Significant pre-existing organ dysfunction prior to randomization
 - a. Lung: Currently receiving home oxygen therapy as documented in medical record
 - b. Heart: Pre-existing congestive heart failure defined as an ejection fraction <20% as documented in the medical record
 - c. Renal: End-stage renal disease requiring renal replacement therapy or eGFR < 30 mL/min.
 - d. Liver: Severe chronic liver disease defined as Child-Pugh Class C (Appendix D) or AST or ALT > 5 times the upper limit of normal
 - e. Hematologic: Baseline platelet count $\leq 50,000/\text{mm}^3$
7. Presence of coexisting infection, including, but not limited to:
 - a. HIV infection not virally suppressed and with pre-hospitalization CD4 count $\leq 500 \text{ cell/mm}^3$
 - b. Active tuberculosis or a history of inadequately treated tuberculosis
 - c. Active hepatitis B or hepatitis C viral infection
8. Ongoing immunosuppression
 - a. Solid organ transplant recipient
 - b. High-dose corticosteroids (equivalent to $>20 \text{ mg/prednisone/day}$) within the past 28 days, except for dexamethasone 6 mg daily or equivalent dose corticosteroid initiated for COVID-19 illness prior to randomization.
 - c. Oncolytic drug therapy within the past 28 days
9. Current treatment, or treatment within 30 days or five half-lives (whichever is longer) with etanercept (Enbrel®), infliximab (Remicade®), adalimumab (Humira®), certolizumab (Cimzia®), golimumab (Simponi®), anakinra (Kineret®), rilonacept (Arcalyst®), tocilizumab (Actemra®), sarilumab (Kevzara®), siltuximab (Sylvant®), or other potent immunosuppressant or immunomodulatory drugs or treatments
10. Current treatment with an anti-viral medication for COVID-19 (e.g. hydroxychloroquine, lopinavir/ritonavir) other than remdesivir
11. Current enrollment in an interventional trial for COVID-19 illness.

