13.1. Overview

This is a double-blind, placebo-controlled randomized study to assess the efficacy and safety of IC14 in COVID-19 participants admitted to an acute care hospital with signs and symptoms consistent with level 5 on the 8-category ordinal scale (OS). Participants will be randomized to IC14 or placebo with 1:1 ratio and followed for 60 days after randomization. The study drug will be administered daily on Days 1-4. The randomization will be stratified by groups of study sites and concomitant use of dexamethasone or equivalent corticosteroid at baseline. All participants will receive baseline antiviral therapy with remdesivir.

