13.8.2.2. Secondary Analysis of Primary Endpoint

The treatment effect represented as the recovery rate ratio will be estimated using Cox proportional hazard regression. The Kaplan-Meier estimates of the recovery proportions over time will be provided to graphically present the data. Covariates to be used in the secondary analysis of the primary endpoint will be specified in the Statistical Analysis Plan and will include age and co-existing diseases, such as hypertension and diabetes mellitus.

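### Criterion 5 does not secure the category 5 population described in Section 13.1, and the primary test takes no account of baseline ordinal category

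*Combined protocol and SAP*

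**What the plan says.** Three places describe who enters.

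- Section 13.1 (Overview) describes patients admitted with "signs and symptoms consistent with level 5 on the 8-category ordinal scale (OS").
- Section 4.1 describes hypoxemic patients "but who are not yet requiring monitoring or support in an intensive care unit".
- Section 4.2, criterion 5, is the operative rule: "Hypoxemia as defined by any of the following". Limb 5a is SpO2 of 94% or less on room air. Limb 5b is a need for at least 2 L/min by standard cannula, "but not requiring high-flow nasal cannula", which is defined as 30 L/min or more. The synopsis has the same two-limb structure.

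In Section 4.3 the respiratory-support exclusions are "Receiving non-invasive positive-pressure ventilation through nasal mask, face mask, or nasal plugs" (exclusion 1) and invasive ventilation (exclusion 2). High-flow cannula is not listed.

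In Appendix C, category 4 is hospitalized without supplemental oxygen but needing ongoing care, category 5 is on supplemental oxygen, and category 6 includes high-flow devices.

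Baseline category is recorded before dosing (8.3.1) and compared between arms descriptively (13.8.5). Randomization is stratified by site group and baseline corticosteroid use (3.4), and the primary log-rank test uses the same two factors (13.8.2.1). The Cox covariates are left to the Statistical Analysis Plan and "will include age and co-existing diseases, such as hypertension and diabetes mellitus" (13.8.2.2).

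**The concern.** The sample size rests on a single placebo recovery curve, and the stated aim is to treat patients before high-level support is needed. If the entry rule lets in categories on either side of 5, two things follow.

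First, recovery times become a mixture. When a log-rank test ignores a strong baseline predictor of recovery, the fast recoverers leave the IC14 risk set sooner than the placebo risk set. The remaining IC14 risk set is then increasingly made up of slow recoverers. This pulls the observed rate ratio toward 1 and costs power.

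Second, high-flow cannula at 30 L/min or more with FiO2 of 0.4 or more is itself a component of acute respiratory failure in Section 3.2.1. A participant on it at entry could already have failed endpoint 5, "Proportion of participants alive-and-free of any episode of acute respiratory failure through Day 28", and would lose days on endpoint 1, whatever the treatment does.

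**Working it through.** **Eligibility, read side by side**

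| Patient at screening | Limb 5a | Limb 5b | Exclusions 1-2 | Result |
|---|---|---|---|---|
| SpO2 94% on room air, no oxygen | met | not met | none apply | eligible, category 4 |
| 2 L/min or more by standard cannula, SpO2 maintained as 5b requires | not needed | met | none apply | eligible, category 5 |
| Now on high-flow; earlier room-air reading 94% or less | met only if the earlier reading counts | barred | none apply | unclear, category 6 |

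The first row follows directly from the wording. The third depends on carrying forward a reading for which 5a sets no date.

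**The plan's own figure**

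Inputs (13.11): RR 1.4, placebo median 6 days, Weibull shape 0.73, 28 days, alpha 0.05 (taken as two-sided), power 80%, 1:1 allocation.

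- Events (Schoenfeld): 4 × (1.960 + 0.842)² / (ln 1.4)² gives 278. The plan states 278.
- Recovery by Day 28: 1 − exp(−ln 2 × (28/6)^0.73 × RR) = 0.882 (placebo) and 0.950 (IC14), as in Table 7.
- N = 278 / ((0.882 + 0.950)/2) = 304. The plan states 302.

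The calculation is sound for one homogeneous curve. The documents do not say which baseline categories the cited remdesivir curve represents, so its match to category 5 cannot be checked.

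**Effect of a mixed population**

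The documents give neither category shares nor recovery rates by category, so both are assumptions here. Simulated trials used N=302, a within-category RR of 1.4, the plan's Weibull curve for category 5, and censoring at Day 28. The log-rank test was run without and with baseline category as a stratum. Site group and corticosteroid strata were not modelled. Relative recovery hazards against category 5 are given for categories 4 and 6.

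| Mix of categories 4/5/6 (%) | Relative hazards (4; 6) | Power, unstratified | Power, stratified |
|---|---|---|---|
| 0/100/0 | n/a | about 79% | about 79% |
| 15/85/0 | 1.5; n/a | about 79% | about 79% |
| 10/85/5 | 1.5; 0.4 | about 75% | about 78% |
| 15/70/15 | 1.5; 0.4 | about 70% | about 78% |

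The range under other assumptions is wide. A 10/85/5 mix with milder hazards (1.5; 0.5) gives 78% unstratified and 80% stratified. A 20/60/20 mix with stronger ones (2.0; 0.35) gives 63% and 78%. With 3,000 replicates, the 95% simulation error near 75% is about 1.96 × √(0.75 × 0.25/3000) = 1.5 points, so differences of a point or two are noise.

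Under the null, the 20/60/20 mix rejected in 5.0% (unstratified) and 5.1% (stratified) of trials.

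**Endpoint 5**

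If a share p is on qualifying high-flow oxygen at entry, and an episode already under way counts, the endpoint cannot exceed 1 − p in either arm: 95% for p = 5%, 85% for p = 15%.

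**The case against.** A reader might infer that the criteria simply admit patients on high-flow oxygen. The text does not go that far. Limb 5a is worded as a current state, and a patient on high-flow is not on room air. Nothing says an earlier reading may be carried forward, and 5b, 4.1 and 13.1 all point the other way. What stands is that none of these closes the route: 5b binds only its own limb, and 4.1 and 13.1 are descriptive.

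A reader might also infer that eligibility is never rechecked. Section 8.2 requires a final determination of the inclusion and exclusion criteria after consent. It does not expressly call for a repeat oxygen assessment, but it is a check. Of the time allowed in Section 3, the 12 hours to first dose come after randomization, so a change in that window is not an eligibility failure.

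Nor can one say that category is adjusted for nowhere. That is established for randomization and the primary test. The Cox covariate list is open, and the Statistical Analysis Plan may add to it.

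Finally, 70% should not be read as this trial's expected power. It needs 15% of participants on high-flow at entry, by a route that looks unintended. At 5% the loss is a few points or less, and if only categories 4 and 5 enter, stratifying gains about a point at most. These limits stand.

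The rule that extends enrollment to 278 recoveries or 350 participants (13.11) is not a full answer. With that rule modelled, the 15/70/15 mix stayed at about 71% unstratified, because the loss comes mainly from dilution rather than too few events.

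**Conclusion.** The point holds in a limited form. Entry in category 4 is certain from the wording and contradicts 13.1, but it costs almost no power. Entry in category 6 is an ambiguity, not a stated rule. If it occurs, it accounts for nearly all of the power loss and also compromises secondary endpoints 1 and 5. A baseline variable likely to predict recovery is collected and left out of the primary test.

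Under the main assumed hazards (1.5 and 0.4), the unstratified test loses between nothing (no category 6) and about 9 points (15% in category 6). Stratifying brings power back to about 78%. The true size depends on shares and recovery rates that the documents do not give. Validity of the test is not in question.

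**What to change.** 1. **Analysis, before unblinding.** Add the recorded pre-dose ordinal category as a stratum of the primary log-rank test (13.8.2.1), pooling site groups if cells are sparse, and name it as a Cox covariate in 13.8.2.2. No new data are needed. The cost is a few more, smaller strata. If high-flow entry is ruled out, the gain is small, and the change is then inexpensive insurance.

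2. **Eligibility text.** The sponsor should reconcile criterion 5 (Section 4.2 and synopsis), exclusions 1-2, Section 4.1 and Section 13.1 on which oxygen-support categories may enter. Which rule is right is for the sponsor to decide. The text should also state that eligibility is confirmed before randomization. Confirming it at the pre-dose baseline assessment instead could remove participants already randomized, because that assessment may fall on Day 1, up to 12 hours after randomization. Section 11.3 does not allow such participants to be replaced. The cost is a wording amendment and possibly a few patients whose eligibility changes.

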4.3. Exclusion Criteria

An individual fulfilling **any** of the following criteria is to be excluded from enrollment in the study:

1. Receiving non-invasive positive-pressure ventilation through nasal mask, face mask, or nasal plugs
2. Receiving invasive mechanical ventilation
3. Patient, surrogate, or physician not committed to full support (exception: a participant will not be excluded if he/she would receive all supportive care other than attempts at resuscitation from cardiac arrest)
4. Anticipated survival < 48 hours

5. Underlying malignancy, or other condition, with estimated life expectancy of less than two months
6. Significant pre-existing organ dysfunction prior to randomization
 - a. Lung: Currently receiving home oxygen therapy as documented in medical record
 - b. Heart: Pre-existing congestive heart failure defined as an ejection fraction <20% as documented in the medical record
 - c. Renal: End-stage renal disease requiring renal replacement therapy or eGFR < 30 mL/min.
 - d. Liver: Severe chronic liver disease defined as Child-Pugh Class C (Appendix D) or AST or ALT > 5 times the upper limit of normal
 - e. Hematologic: Baseline platelet count $\leq 50,000/\text{mm}^3$
7. Presence of coexisting infection, including, but not limited to:
 - a. HIV infection not virally suppressed and with pre-hospitalization CD4 count $\leq 500 \text{ cell/mm}^3$
 - b. Active tuberculosis or a history of inadequately treated tuberculosis
 - c. Active hepatitis B or hepatitis C viral infection
8. Ongoing immunosuppression
 - a. Solid organ transplant recipient
 - b. High-dose corticosteroids (equivalent to $>20 \text{ mg/prednisone/day}$) within the past 28 days, except for dexamethasone 6 mg daily or equivalent dose corticosteroid initiated for COVID-19 illness prior to randomization.
 - c. Oncolytic drug therapy within the past 28 days
9. Current treatment, or treatment within 30 days or five half-lives (whichever is longer) with etanercept (Enbrel®), infliximab (Remicade®), adalimumab (Humira®), certolizumab (Cimzia®), golimumab (Simponi®), anakinra (Kineret®), rilonacept (Arcalyst®), tocilizumab (Actemra®), sarilumab (Kevzara®), siltuximab (Sylvant®), or other potent immunosuppressant or immunomodulatory drugs or treatments
10. Current treatment with an anti-viral medication for COVID-19 (e.g. hydroxychloroquine, lopinavir/ritonavir) other than remdesivir
11. Current enrollment in an interventional trial for COVID-19 illness.
12. History of hypersensitivity or idiosyncratic reaction to IC14 or any other monoclonal antibody.
13. Women who are currently breast feeding.
14. Received a live-attenuated vaccine within 30 days prior to enrollment.
15. Received five or more doses of remdesivir, including the loading dose, outside of the study as treatment for COVID-19
16. Any condition that in the opinion of the treating physician will increase the risk for the participant

5. Known and Potential Risks and Benefits to Participants

5.1. Risks of Investigational Product in Clinical Studies

To date, 168 healthy volunteers and patients have received IC14, across a range of clinical studies, LPS challenge (Verbon 2001), community-acquired pneumonia (Axtelle et al. 2003), sepsis (Reinhart et al. 2004;), acute lung injury, and amyotrophic lateral sclerosis. IC14 was generally well tolerated. Adverse events that were at least 5% more common in participants receiving IC14 compared to placebo (regardless of whether they were considered related to IC14 or were due to the underlying disease) are below:

Table 1. Adverse Events Observed with IC14

Side Effect	How often is it likely to occur?	How severe might it be?	How long might it last?
Low platelets (blood clotting cell)	8.3% (2.7% in placebo)	mild-moderate	One week

One SAE occurred (hypotension and rash) in a treated patient with sepsis, which resolved with ranitidine, dimetindine, and prednisolone.

No anti-drug antibodies have been detected in 168 participants treated with IC-14.

In separate randomized placebo-controlled studies of patients with community acquired pneumonia, sepsis or ARDS the number of patients thought to have new bacterial infections after beginning IC14 treatment was balanced across placebo and IC14 groups. In addition, hepatobiliary and renal failure serious adverse events occurred more often with IC14 than placebo (hepatobiliary events 3.8% in IC14 vs. 0% in placebo; renal failure events 5.3% in IC14 vs. 0.9% in placebo).

In studies of IC14 in non-human primates, small numbers of vitreous cells were noted in animals treated with IC14 daily for 14 days that resolved over the following 28 days. These changes were not associated with pathological findings in the eyes and were considered of minor toxicological significance. Eye findings have not been observed in 63 human participants treated with IC14 who had one or more ophthalmologic and/or slit lamp examinations and there were no pathological findings in the eyes of 20 non-human primates that were treated with weekly intravenous doses of either 20 mg/kg/week or 50 mg/kg/week for 26 weeks.

5.2. Risks of Investigational Product Cited in Medical Literature

There is a theoretical risk of immunosuppression with IC14 treatment, although this has not been reported in the medical literature. Medications that cause immunosuppression make patients more susceptible to certain kinds of infections, including bacterial infection. Because IC14 does not block a number of alternative pathways that can be used by the host to respond to infection (e.g., complement), it is not broadly immunosuppressive and the number of participants with secondary bacterial infections has not been increased in clinical trials of IC14. Nevertheless, treatment with IC14 could lead to secondary bacterial infections necessitating treatment with antibiotics, treatment in the ICU, or death. It is possible that IC14 might make COVID-19 worse, which could result in worsening respiratory failure, admission to the ICU, or death.

Monoclonal antibodies carry the risk of infusion reactions and in some cases have been reported to cause cytokine storm. In 168 healthy participants and participants with infections treated with IC14, one subject developed an infusion reaction (hypotension and rash), which was successfully treated with ranitidine, dimetindine, and prednisolone. IC14 does not cause cellular activation in vitro and no episodes resembling cytokine storm have been reported in the 168 treated participants treated with IC14.

5.3. Risks of Other Protocol Specified Medications

Participants in this study will be treated with remdesivir, an antiviral medication that has been shown to reduce the time to recovery in hospitalized patients with COVID-19 illness (Beigel et al. 2020). In a recent randomized placebo-controlled trial of remdesivir in hospitalized patients with COVID-19 illness, AEs and SAEs were numerically less frequent in the remdesivir vs. the placebo group. The most common AEs (>5%) in the remdesivir group were decreased hemoglobin (7.9%) and decreased GFR/increased creatinine (7.4%), but these were either more common or numerically similar in the placebo group (9.0% and 7.3%, respectively). In a randomized, open-label trial comparing 5 or 10 days of remdesivir

for moderate COVID-19 pneumonia (i.e. radiologic pulmonary opacities with SpO₂ > 94%) against standard care (Spinner 2020: PMID: 32821939) serious adverse events were less common in the remdesivir groups (5% in both) than in the standard care group (9%). Adverse events were experienced by 51% of patients in the 5-day remdesivir group, 59% in the 10-day remdesivir group, and 47% in the standard care group. Adverse events that were more common in the remdesivir groups than in the standard care group included nausea, hypokalemia, and headache.

It is likely that many participants in this study may be treated with dexamethasone or an equivalent corticosteroid at baseline, or if they worsen during the study, because of the results of the RECOVERY trial (Recovery 2020). There is a theoretical risk that concomitant use of dexamethasone and IC14 could increase the risk of secondary infections, although there are no data to support this at the present time. This will be a common risk for all participants with COVID-19 who are treated with corticosteroids and a biological response modifier. At present there are no preclinical or clinical studies in which IC14 has been evaluated in the presence of dexamethasone or other corticosteroids.

